Secondary Aim: To describe the effects of fenofibrate monotherapy on lipoprotein particle number and size by nuclear magnetic resonance spectroscopy performed in non-responders and responders at 2 months of treatment, when drug treatment will be discontinued for lack of efficacy to agent. Lipids in responders and control groups will be studied by NMR spectroscopy at 4 months of treatment, which will be at the termination of the proposed treatment period.

Tertiary Aim: To determine the safety of fenofibrate monotherapy. Documentation and description of adverse events will be obtained in subjects who have received drug treatment compared to events occurring in the control group.

Target Population

It is estimated that approximately 100 participants with SCI will be screened to identify 30 eligible and appropriate SCI participants (i.e., 20 treatment, 10 control) who will agree to participate in the study (Screening data from BAU-11-075 will be used to minimize the number of procedures performed, if it is not older than 45 days). To be considered eligible for the study, participants must meet the following eligibility criteria:

Inclusion Criteria:

- (1) Male or female, age 21 to 69;
- (2) Chronic (e.g., duration of injury at least 6 months), stable SCI (regardless of level of neurological lesion);
- (3) American Spinal Injury Association Impairment Scale (AIS) designation of A, B or C; and
- (4) TG concentration ≥ 135 mg/dl (paraplegia) or ≥ 115 mg/dl (tetraplegia).

Exclusion Criteria (These exclusion criteria were carefully chosen to minimize subject risk and/or confounding factors that are known to affect study endpoints):

- (1) Acute illness or infection;
- (2) Reduced kidney function (by glomerular filtration rate (GFR < 60 ml/min) or liver function tests (LFTs ≥ 2.5 times above the upper limit of normal) as determined by test results at screening and any time point of the study;
- (3) Current pharmacological treatment with: HMG-CoA reductase inhibitors (statins), or any other hypolipidemic agent; anti-coagulant therapy; cyclosporine; or any other medications known to effect the TG concentration (i.e., β -blockers, thiazides or estrogen);
- (4) Hypersensitivity to fenofibrate;
- (5) Existing diagnosis of atherosclerosis, congestive heart failure, or recent history of myocardial infarction (i.e., ≤ 12 months);
- (6) Pregnancy or women who may become pregnant during the course of the study, or those who are nursing;

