The proposed investigation is an open-label, parallel-group intervention and randomized trial to determine the safety and efficacy of fenofibrate monotherapy on the lipoprotein profile in persons with SCI. A screening visit will be performed in up to 100 persons with SCI to identify 30 subjects who have adverse TG concentrations (i.e., paraplegia: ≥ 135 mg/dl; tetraplegia ≥ 115 mg/dl). After a baseline evaluation, a comprehensive medical history review and intake interview will be performed to identify demographic information, current health status, medications and lifestyle habits (i.e., smoking, alcohol consumption, recreational drug use, physical activity habits, diet etc.). Twenty subjects with adverse TG concentrations will be randomized to receive once daily fenofibrate therapy (i.e., 145 mg) for 4 months (dispensed by the research pharmacy of the James J. Peters VA Medical Center) and the remaining 10 subjects with adverse TG concentrations will receive no treatment and will serve as control subjects. All subjects will complete monthly follow-up visits for the study period, which also includes a 1-month post-treatment visit. If after 2 months of continuous fenofibrate treatment a subject does not demonstrate an improvement of $\geq 25\%$ in TG concentration, then he/she will be discontinued from the study drug under appropriate supervision and terminated from the study. For those who respond to fenofibrate treatment, he/she will continue on treatment for an additional 2 months.

The primary study outcome will be to determine the efficacy of treatment on the serum lipoprotein profile (i.e., TG, HDL-C, LDL-C, total cholesterol), and the secondary study

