outcome will be the lipoprotein particle number and size by NMR (i.e., HDL, LDL and VLDL subfractions). Liver (enzymes: AST, ALT, GGT) and kidney function (i.e., glomerular filtration rate) tests, and a complete blood count (CBC) with differential will be performed at all study visits, from blood samples, respectively, to monitor subject safety (Table 2). To facilitate our understanding of the relationship between metabolic parameters, body composition and primary study outcome measurements associated with treatment efficacy, a 2 hour oral glucose tolerance test, and a total body dual energy x-ray absorptiometry (DXA) scan will be performed to quantify total body fat mass and fat-free mass at baseline, as well as to determine visceral adipose tissue volume (enCore™ software (Lunar iDXA, platform version 13.6, General Electric Medical Systems, Madison, WI) at baseline and at 4 months. In addition, all subjects who enter the trial as a treatment or control subject will receive dietetic counseling at baseline and at 2 months. Study support staff will perform phone calls twice a month to monitor drug compliance and direct concerns to the study physician during intervals when there may be noncompliance with scheduled study follow-up visits. Thus, the proposed research investigation incorporates and follows best practices for the clinical treatment and utility of fenofibrate monotherapy in persons with dyslipidemia.

Table 2. Table of Procedures

	Screening	Baseline	Treatment				Follow-Up
			Month 1	Month 2	Month 3	Month 4	Post- 1 month
Safety Labs							
Liver and Kidney Function	x	x	x	x	x	x	x
CBC with Differential	x	x	x	x	x	x	x
Primary Study Outcomes							
Lipoprotein Concentrations	x	x	x	x	x	x	x
Lipoprotein Particle Number		x	x	x	x	x	x
Additional Outcomes							
Fasting Insulin, Glucose and A1	x	x	x	x	x	x	x
Oral Glucose Tolerance Test		x				x	
Body Composition Analysis		x				x	
ApoE blood genotyping		x					

Procedures

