The health risks associated with this research study are minimal in nature. As with any investigational study, there may be adverse events or side effects that are currently unknown. In the case of a serious adverse event during the test, hospital emergency personnel will be summoned over telephone by study personnel. The following list contains potential risks/and or discomfort related to study procedures:

-Fenofibrate: Common side effects for treatment include abdominal pain, skin rash, and nausea. Less common side effects include gas, bloating, change in bowel frequency and stool color. As mentioned previously participants are at risk to develop elevated and/or abnormal liver and kidney function from taking Fenofibrate. If abnormal levels become evident as indicated by safety monitoring labs taken at each time point, the subject will be discontinued from study drug and monitored on a monthly basis for up to four months or until liver function returns to normal. In addition, if the subject develops elevated and/or abnormal liver function results, they may experience the following: yellowing of eyes/skin, dark urine, pruritis, swelling, and headache.

-Blood draw/catheter placement: The subject may experience the feeling of being lightheaded, dizzy, blurry eyesight, nausea and/or syncope during the needle/catheter insertion. There is also the potential risk of developing a bruise or infection at the site of skin puncture.

-Oral glucose tolerance test: In addition to the listed risks for blood draw/catheter placement, the ingestion of a large volume of glucose may cause some individuals to experience nausea.

-Dual energy x-ray absorptiometry scans: To complete the scan, participants will be asked to transfer from their wheelchair to the scanning bed. This will be completed independently or with assistance from an overhead patient lift. The scan will take approximately 15 minutes to complete during which the subject will be asked not to move. Each dual energy x-ray absorptiometry scan will expose the subject to 8.62 μ Sv of radiation (i.e., equivalent to 1/5 of an average chest x-ray), thus each subject will receive 17.24 μ Sv for the two scans.

Statistical Analyses

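### Twice-monthly drug-compliance calls appear to reach only the fenofibrate arm routinely, so self-reported adverse events would be ascertained unequally between arms

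*Combined protocol and SAP*

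**What the plan says.** The Methods section describes an "open-label, parallel-group intervention and randomized trial to determine the safety and efficacy of fenofibrate monotherapy". Allocation is "20 treatment, 10 control" (Target Population). There is no placebo: "the remaining 10 subjects with adverse TG concentrations will receive no treatment and will serve as control subjects".

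Visits follow the same schedule in both arms: "All subjects will complete monthly follow-up visits for the study period, which also includes a 1-month post-treatment visit". The Methods section then adds the calls: "Study support staff will perform phone calls twice a month to monitor drug compliance and direct concerns to the study physician". The same sentence ends "during intervals when there may be noncompliance with scheduled study follow-up visits". It does not name the recipients. The sentence just before it, on dietetic counselling, names treatment and control subjects explicitly.

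The Tertiary Aim (Goals and Objectives) makes safety a between-arm comparison: "Documentation and description of adverse events will be obtained in subjects who have received drug treatment compared to events occurring in the control group". Under Potential Risks, "Common side effects for treatment include abdominal pain, skin rash, and nausea", and gas and bloating are listed as less common.

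The document does not say how adverse events are elicited at visits or on calls, and Statistical Analyses contains no adverse-event analysis. Treated subjects whose triglycerides have not improved enough at 2 months are terminated from the study (Methods).

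**The concern.** Most of the listed side effects are mild symptoms that enter the record only if the subject mentions them. A subject who speaks to study staff three times a month has more chances to mention a passing symptom, and less time to forget it, than one seen once a month. A call about tablet-taking, made by staff who pass concerns to the physician, invites such reports even if nobody asks about symptoms. No rule keeps what is reported on calls out of the between-arm comparison.

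If only treated subjects are called, an excess of mild events per month on fenofibrate could come from the drug, from the extra contact, or from both, and the data could not separate them. With 20 against 10 subjects, a few differentially recorded events could shape the safety conclusion.

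**Working it through.** The plan states no contact ratio, adverse-event rate or safety sample size, so it gives no figure to reproduce. The check counts contacts and then asks what they could do to recorded events.

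**Inputs from the document.** Visits: 1 per month in both arms. Calls: 2 per month. Treatment period: 4 months. Treated non-responders leave at month 2. Arms: 20 and 10. **Assumed inputs.** The responder share *r* and the mean time *m* for which a mild symptom is remembered; the document gives neither.

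**Step 1: contacts per month while in follow-up.**

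| Reading of the call sentence | Treated | Control | Ratio |
|---|---|---|---|
| Only treated subjects called, every month | 1 + 2 = 3 | 1 | 3.0 |
| Both arms called | 3 | 3 | 1.0 |
| Calls only around missed visits, either arm | not fixed | not fixed | not fixed (calls partly replace visits) |

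The first reading fits the compliance purpose best. It also gives the largest ratio, so 3 to 1 is an upper bound.

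**Step 2: contacts over the treatment period, treated-only calls.** A responder has 4 × 3 = 12 contacts, a non-responder 2 × 3 = 6, and a control 4. The average per treated subject is 12*r* + 6(1 − *r*):
- *r* = 0: 6/4 = 1.5
- *r* = 0.5: 9/4 = 2.25
- *r* = 1: 12/4 = 3.0

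If the post-treatment visit is counted and calls stop at month 4, a responder has 13 contacts against 5 for a control, a ratio of 2.6.

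**Step 3: from contacts to recorded events (illustration).** Suppose an event occurs at a random time between contacts *g* days apart and is still reported at the next contact with probability exp(−time/*m*). The share recorded is (*m*/*g*)(1 − exp(−*g*/*m*)). Take *g* = 10 days for treated subjects and 30 days for controls, with equal true rates. *R* is the ratio of shares, computed before rounding:

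| Mean recall *m* | Treated share | Control share | *R* per person-month |
|---|---|---|---|
| Perfect | 1.000 | 1.000 | 1.0 |
| 30 days | 0.850 | 0.632 | 1.35 |
| 14 days | 0.715 | 0.412 | 1.73 |
| 7 days | 0.532 | 0.230 | 2.31 |
| Near zero | – | – | approaches 3.0 |

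Under this model the rate per month on study is never deflated in the drug arm, and is inflated unless recall is perfect.

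**Step 4: crude events per subject.** Treated observation averages 2 + 2*r* months on the 4-month schedule, against 4 for controls. The crude ratio is *R*(2 + 2*r*)/4. At *r* = 0.5 it is 0.75*R*, that is 0.75 to 2.25 as *R* runs from 1.0 to 3.0. Over all *r* the range is 0.5 to 3.0. With *r* = 0.5 and *m* = 30 days it is 1.01, so the two distortions nearly cancel.

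**Step 5: after equalising the calls.** Contacts are 3 per month in each arm and *R* = 1.0. The length factor (2 + 2*r*)/4 remains, 0.75 at *r* = 0.5. It needs person-time rates or a common window.

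**The case against.** **Who is called is not stated.** The document never says that controls are not called. The closing clause on missed visits could bring in some controls, or could limit the calls, or the passing on of concerns, to such periods. This stands, and it is why 3 to 1 is only an upper bound. The clause does not, however, give controls a matching schedule.

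**The calls are not described as adverse-event inquiries.** A reader might infer that adverse events are looked for three times as often in the drug arm. The document does not support that: three is a ratio of contacts, and Step 3 shows that recorded events could differ by far less. Nor would it be right to give each event three independent chances of being recorded, since a call on day 10 cannot pick up an event on day 25.

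**Scheduled laboratory safety is unaffected.** Liver, kidney and blood-count tests are done at every study visit with no distinction by arm (Methods, Table 2). The point concerns symptoms only.

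**The net direction is not fixed.** A reader might infer that the whole safety comparison is biased against the drug. Early departure of treated non-responders pulls crude totals the other way (Step 4). Two opposing distortions still do not make a fair comparison.

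**The aim is descriptive.** No test of adverse events is specified, which lowers the stakes. A descriptive table of the two arms still needs events collected in the same way.

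**An effect on triglycerides through diet.** A reader might also infer that the calls reinforce dietary advice in one arm. Nothing says that diet is discussed on calls, and counselling is given to both arms, so this is speculation.

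**Equal calls do not cure open-label reporting.** Subjects who know they take a drug may report more symptoms. That remains after the fix, which removes one source of bias and not all of them.

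**Conclusion.** The concern holds in limited form. On the natural reading only the fenofibrate arm is called routinely, which gives up to 3 contacts per month against 1 while subjects are in follow-up. With no common inquiry described, this makes ascertainment of self-reported symptoms unequal and tends to inflate their rate per month on study in the drug arm. The size is unknown: the illustrative ratios of 1.35 to 2.31 depend wholly on assumed recall times of 30 to 7 days, and the possible range is 1.0 to just under 3.0. The conclusion rests on treated-only calls, which is an inference from the compliance purpose, and on symptoms mentioned during calls being recorded as adverse events. It does not extend to scheduled laboratory findings, to the net direction of crude totals, or to the lipid outcomes. It should be corrected, because the remedy is cheap; confidence is medium.

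**What to change.** State in Methods that the twice-monthly calls go to all 30 subjects on the same schedule. Open each call with the same scripted, open question about new symptoms, and ask about tablets only in treated subjects, at the end. Cost: at most about 10 controls × 2 calls × 4 months = 80 extra short calls by the same staff.

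If controls are not to be called, base the between-arm comparison on events elicited by that same question at the monthly visits, and list call-reported events separately. This needs no extra contacts. The downsides are fewer events in the comparative table, and that earlier calls may still prompt treated subjects' recall at visits.

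Under either option, add to Statistical Analyses that adverse events are reported per person-time or over the common first two months, so that the early departure of treated non-responders does not distort the totals.

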Safety Labs: Serum blood specimen will be obtained for the determination of the glomerular filtration rate (GFR). If at screening or during the trial, GFR is <60 ml/min, the potential subject will not be eligible to enroll in the study, or if the GFR should fall to <60 ml/min during the trial, the participant will be discontinued from study drug; renal function will be monitored for a period of at least 4 months after identifying a fall in creatinine clearance while on study drug. Liver function tests [i.e., AST, ALT (<35 IU/L), GGT (elevated for respective age and

gender)] and complete blood count with differential (CBC with diff) will be obtained and evaluated for abnormal values. If evidence for abnormal liver function (i.e., 2 standard deviations above the upper limit of normal) or infection (white blood cell >10,000 cells/ml), the subject will either be considered ineligible for the study at the time of screening or discontinued from study drug under appropriate supervision and monitored for a period of at least 4 months. These specimens will be processed by a commercial laboratory at the time of collection (LabCorp). All safety labs will be reviewed by [name] (Co-Investigator and study physician). He will be responsible for the oversight of safety monitoring, eligibility and review of all laboratory data from screening and treatment.

Primary Study Outcomes: Venous blood samples will be obtained after an overnight fast (minimum 8 hours) for the determination of lipoprotein concentrations (i.e., HDL-C, LDL-C, VLDL-C, TG and total cholesterol) and lipoprotein particle number and size (i.e., mean size of HDL, LDL and VLDL particle; the number of HDL, LDL and VLDL for the respective sub-fraction of small, medium and large particles). Lipoprotein concentrations will be processed by a commercial laboratory at the time of collection (LabCorp); lipoprotein particle number and size will be performed as a fee-for-service by Liposcience, Inc (Raleigh, NC, USA).

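### The white-cell limit for infection is printed in cells/ml, 1,000 times below the evidently intended cells/µL

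*Combined protocol and SAP*

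**What the plan says.** Under Procedures, the Safety Labs paragraph gives the only numerical definition of infection in the document: "infection (white blood cell >10,000 cells/ml". The consequence follows in the same sentence: "the subject will either be considered ineligible for the study at the time of screening or discontinued from study drug under appropriate supervision". Subjects who are stopped are then monitored for at least 4 months.

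The limit comes into play repeatedly. The Methods section states that a "complete blood count (CBC) with differential will be performed at all study visits", and Table 2 marks it at screening, baseline, months 1 to 4 and the post-treatment visit.

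Two statements under Target Population bear on how the limit should be read. Exclusion criterion 1 is simply "Acute illness or infection", with no count and no unit. The recruitment plan is that "approximately 100 participants with SCI will be screened to identify 30 eligible and appropriate SCI participants".

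The Safety Labs paragraph also makes a study physician "responsible for the oversight of safety monitoring, eligibility and review of all laboratory data".

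**The concern.** A white-cell limit of 10,000 is recognisable as a count per microlitre. Per millilitre it is a thousandth of that, a level that essentially any blood sample would exceed. The figure is a decision rule: it determines who may enter and who must stop fenofibrate. As printed, it would turn away practically everyone at the screening blood count, and anyone on drug would have to stop at the next count. If the study team in fact applied the sensible limit, essentially every enrolled subject would be in breach of the written rule. Someone auditing the trial or reusing the protocol would find no correct value elsewhere in the text.

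**Working it through.** **Inputs**

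- Printed limit: >10,000 cells/ml (Procedures, Safety Labs).
- Planned yield: about 100 screened, 30 enrolled (Target Population).
- Ordinary adult white-cell count: about 4,000 to 11,000 cells/µL. This is an assumption. The documents give no reference range, so much lower counts, down to 500 cells/µL, were tried as well.

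The plan derives no figure from this limit, so there is no calculation of its own to reproduce. The check is a unit conversion.

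**Step 1: the printed limit per microlitre.** 1 ml = 1,000 µL, so 10,000 cells/ml ÷ 1,000 = 10 cells/µL.

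**Step 2: the evidently intended limit.** 10,000 cells/µL × 1,000 = 10,000,000 cells/ml. The ratio to the printed limit is 10,000,000 ÷ 10,000 = 1,000. In SI form, 10,000 cells/µL × 10^6 µL/L = 10 x 10^9 cells/L.

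**Step 3: who would be flagged.** Multiply each count by 1,000 to get cells/ml, then divide by 10,000.

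| Count (cells/µL) | Count (cells/ml) | Multiple of printed limit | Flagged as printed | Flagged at >10,000 cells/µL |
|---|---|---|---|---|
| 500 | 500,000 | 50 | yes | no |
| 1,000 | 1,000,000 | 100 | yes | no |
| 2,000 | 2,000,000 | 200 | yes | no |
| 4,000 | 4,000,000 | 400 | yes | no |
| 7,000 | 7,000,000 | 700 | yes | no |
| 11,000 | 11,000,000 | 1,100 | yes | yes |

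As printed, the rule flags every count tried and cannot tell an infected subject from a healthy one. In cells/µL it separates them as a limit for infection should.

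**Step 4: effect on enrolment.** The planned yield is 30/100 = 30%. Under the literal limit it is about 0%, because any count above 10 cells/µL is a breach. The result hardly depends on the assumed range, since even 500 cells/µL is 50 times the limit.

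**Step 5: is it corrected elsewhere?** Exclusion criterion 1 names infection without a count. Potential Risks describes stopping drug for abnormal liver or kidney results and gives no white-cell limit. Table 2 lists the blood count without a threshold. Nothing supplies the right value.

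**The case against.** The strongest objection is that the slip has no consequence. A commercial laboratory processes the samples, a physician reviews every result, and infection is also a clinical exclusion in its own right. The literal rule would reject everybody at the first screening count, so it would reveal itself at once. Randomisation, the triglyceride response definition, the sample size and the analyses do not use the number. All of this stands, and it is why the point is minor. It does not make the written limit right.

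The second objection is that the whole point turns on one character, and the program that read the PDF may have turned µ into m. The extracted text does treat symbols unevenly, with stray spaces around some Greek letters and some inequality signs rendered as markup. Against that, the micro sign survives in the radiation dose under Potential Risks ("17.24 μ Sv for the two scans"), β survives in exclusion criterion 3 and α in the Scientific Abstract. A misreading is therefore possible but less likely. It cannot be excluded without the source page.

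A third objection is that the plan alone does not prove which unit was meant: the recruitment target conflicts with 10 cells/µL only for a reader who knows that ordinary counts are far higher. That is fair as to reasoning, and the range is labelled as an assumption for this reason. The conclusion survives any count above 10 cells/µL.

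**Conclusion.** The limit is wrong as written, by a factor of exactly 1,000. The factor is pure arithmetic. That cells/µL was meant, and that a literal reading would leave essentially 0 of about 100 screened eligible instead of 30, rests on adult white-cell counts being far above 10 cells/µL, a figure the documents do not give. The point also assumes that the extracted text matches the source page, so confidence is medium.

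The importance is low. The physician would very likely use the right limit, and no result depends on it. It remains worth correcting because it governs eligibility and stopping of study drug at every scheduled blood count and is the only white-cell limit in the document.

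**What to change.** First look at the source page to see whether it reads ml or µl. If it reads µl, nothing needs to change. If it reads ml, amend the Safety Labs paragraph so that the infection limit is a white blood cell count >10,000 cells/µL, i.e. >10 x 10^9/L. Giving both units guards against the same slip recurring.

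The cost is a unit correction in one line. No visit, sample or analysis changes.
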